4.0 OBJECTIVES

4.1 Primary Objectives:

- Mental wellness before and after intervention in the intervention and control groups. A validated Emotional Thermometer Scales will be used to predict changes in parameters reflecting participants' mental health pre- and post-intervention. Survey questions focused on symptoms of depression and anxiety will be used to monitor for changes in mental wellness pre- and post-intervention.

4.2 Secondary Objectives:

- Comparison of mood scores, depression and anxiety symptoms versus frequency of attendance in the intervention arm.
- Comparison of somatic symptom burden between intervention and control group.
- Difference in mood scores, depression symptoms, anxiety symptoms, and somatic symptoms after workshop between genders.
- Difference in mood scores, depression symptoms, anxiety symptoms, and somatic symptoms between patients living alone versus with family.
- Difference in mood scores, depression symptoms, anxiety symptoms, and somatic symptoms between various cancer types.
- Difference in mood scores, depression symptoms, anxiety symptoms, and somatic symptoms in individuals who have previously attended a creative writing class versus those who have not.
- Difference in mood scores, depression symptoms, anxiety symptoms, and somatic symptoms in individuals who completed control group activity and then enrolled in the workshops and attended at least one session.
- Comparison of the frequency of emergency room visits and hospitalizations between intervention and control group during the study period.

Institutional Review Board

- Comparison of cancer status (stable, progressing, in remission) between intervention and control group.

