There is a substantial area of agreement that language, narrative storytelling, forms an essential element in the construction of a coherent identity, sense of self and connectedness to others, and therefore, it is a powerful tool in creative therapy (Smyth, 1998; Wright & Chung, 2001). Roe and Davidson (2005) argue that processes of re-authoring one's life story are actually integral components of the recovery process itself. A study by Stanton (2002) of breast cancer patients prompted to write about their cancer experience showed a significant decrease in self-reported somatic symptoms and medical appointment visits for cancer-related morbidities three months after participation in the study. A follow-up study by Stanton (2013) encouraged breast cancer patients to create personal websites to chronicle their experience and to communicate with their social network. This study showed significant improvement in positive mood and depressive symptoms after 6 months, particularly in patients undergoing medical therapy at that time. These studies further support that the act of narrative story telling can improve patient wellbeing.

Furthermore, King et al. (2012) suggest that writing can contribute to repair of symbolic functioning and contribute to the development of personal identity. The researchers concluded that, of all the creative arts, writing is least dependent on equipment and/or special environments. Writing workshops are probably better provided by professional writers than by mental health professionals. When health professionals provide activities such as a writing workshop, there is a risk that identification with the illness is reinforced. On the other hand, when a professional writer provides a similar activity, it is the participant's identity as a writer that is reinforced, rather than their identity as a person with an illness. (King et al., 2012)

Moreover, there is emerging consensus in the UK and USA that there might be advantages if writing therapy is received from facilitators who themselves are trained writers and can work in collaboration with health care professionals. (Hunt & Sampson, 1998; Mc Loughlin, 2004).

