9.4.3 Exploratory endpoints

- Difference in number of emergency room visits and hospitalizations during study period between control and intervention group.
- Comparison of status of cancer (stable, progressing, in remission) between intervention and control group.

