10.0 STUDY PROCEDURES

10.1 Methods: After enrollment as above, co-investigators of this study or the assigned coordinator will be doing the consent. Patient will be randomized to intervention and control arms in a 2:1 ratio. The intervention arm will receive a dedicated workshop for one and a half hours every 2 weeks. We aim to start a 6 month long program with weekly creative writings workshops, and patient enrollment in the study will continue through the 1st 4.5 months of the 6 month period so that the last enrolled patient could complete 2 classes per month for two months. Each patient will be asked to attend at least two classes per month for a total of two months. These workshops will be held at Hershey Medical Center (HMC). At the initiation of the study along with consent we will collect baseline scores in both groups for each parameter as below. Somatic Symptom Burden (SSM-8 - Figure 2 - reference section), depression symptoms using PHQ-9 (Figure 3 – reference section), and anxiety symptoms using GAD-7 (Figure 4 – reference section) will be collected monthly and following intervention completion.

We will collect mood scores pre and post each session. We will use Emotional Thermometer Scale (EMS) from [name] (Feb. 2010), diagram for scales is shown in figure 1. Please see supplementary index for a letter of permission to use from [name]. We will give the Thermometer scales and collect scores pre and post each session and also collect scores pre and post completion of entire course. Control group will do EMS on monthly basis along with other parameters. At the end of the study we will review all participants' medical charts to count view the number of emergency room visits and hospitalizations each participant experienced during the study period. These will be further broken down in categories based on cancer

Institutional Review Board

related vs non-cancer related visits. We will also review their most current cancer disease status after completion of the workshops and categorize whether their status is considered to be stable, progressing, or in remission. Both groups will also receive follow up mood and symptom surveys twice a month for up to 2 months after completion of the participant's two to three month study period.

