15.2 Potential Study Benefits

Participants randomized to the intervention with creative writing workshops may experience an improvement in their mood. We suspect that patients may have better adherence to their cancer therapy, but we do not expect any effect on cancer overall.

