22.0 TABLES and FIGURES for the STUDY**Table 1: DEMOGRAPHICS**

Participant	1	2	3	4	5	6	7...
Serial Number							
Alphanumeric code							
Medical Record Number							
Gender							
Age							
Living Alone vs with family/caretaker							
Primary Cancer Type							
Cancer Stage							
ECOG Performance Status							
Enrolled in the Exercise Study							
Regular exercise on or off the exercise study- >30mins three times a week							
Current Treatment (Surgery, Radiation, Chemo)							
Disease status at completion of study (Stable, Progression, Remission)							
Psychiatric history (previous diagnoses or hospitalizations)							
Current Psychiatric Medications							

Figure 1: Emotion Thermometer Score (ETS)

Emotion Thermometers 5 items+help

Instructions: In the first four columns, please mark the number (0-10) that best describes how much emotional upset you have been experiencing in the past week, including today. In the last column please indicate how much you need help for these concerns.

1. Distress	2. Anxiety	3. Depression	4. Anger	5. Need Help
 An orange thermometer with a scale from 0 to 10. The bulb at the bottom is orange and the stem is orange. The top of the stem has three orange radiating lines. The number 10 is at the top and 0 is at the bottom.	 A green thermometer with a scale from 0 to 10. The bulb at the bottom is green and the stem is green. The top of the stem has three green radiating lines. The number 10 is at the top and 0 is at the bottom.	 A blue thermometer with a scale from 0 to 10. The bulb at the bottom is blue and the stem is blue. The top of the stem has three blue radiating lines. The number 10 is at the top and 0 is at the bottom.	 A red thermometer with a scale from 0 to 10. The bulb at the bottom is red and the stem is red. The top of the stem has three red radiating lines. The number 10 is at the top and 0 is at the bottom.	 A grey thermometer with a scale from 0 to 10. The bulb at the bottom is grey and the stem is grey. The top of the stem has three grey radiating lines. The number 10 is at the top and 0 is at the bottom.
Extreme				Desperately
None				Can manage by myself

Are you already getting help for these problems? N/A No Yes Do you want further help for these problems? No Yes

Alex J Mitchell © 2013

Figure 2: Somatic Symptom Scale

Somatic Symptom Scale – 8 (SSS-8)

During the past 7 days , how much have you been bothered by any of the following problems?					

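### The hospitalization count mixes scheduled treatment admissions with unplanned ones, which dilutes any workshop effect on that count

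*Combined protocol and SAP*

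**What the plan says.** Section 10.1 (Methods) plans a chart review of all participants at the end of the study, to "count view the number of emergency room visits and hospitalizations each participant experienced during the study period". The next sentence, interrupted by a page footer, gives the only breakdown: "These will be further broken down in categories based on cancer" and then "related vs non-cancer related visits". Nothing there or elsewhere separates scheduled from unscheduled admissions, or records how a patient came to be admitted.

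Section 9.4.3 lists the comparison as exploratory: "Difference in number of emergency room visits and hospitalizations during study period between control and intervention group". Section 4.2 lists it among the secondary objectives: "Comparison of the frequency of emergency room visits and hospitalizations between intervention and control group during the study period". Section 11.1 sets out mixed models for the four questionnaire groups. It names no analysis for these counts, and it does not say whether emergency visits and hospitalizations are added together or reported apart.

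The file holds three copies of the protocol, and the counting text is the same in each.

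**The concern.** Patients on active treatment can enrol. Section 7.3 admits any cancer diagnosis, section 10.2 collects the chemotherapy regimen, and Table 1 in section 22.0 records surgery, radiation and chemotherapy as current treatment. Some participants may therefore be admitted by appointment during the study. Such an admission mainly reflects the treatment plan.

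The one utilization result cited in the background (5.1) is from a writing trial in breast cancer, which reported a decrease in "medical appointment visits for cancer-related morbidities three months after participation in the study". Section 15.2 adds that "we do not expect any effect on cancer overall". Read together, these suggest that a benefit, if there is one, would show in unplanned use. The cause split does not isolate it, because a planned operation and an unplanned complication are both cancer related. At stake is a hospitalization ratio closer to 1 than the effect on unplanned admissions, with no recorded field that would let an analyst separate the two afterwards.

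**Working it through.** **The plan's own figure.** The only power statement (11.2) is at least 80% for 0.45 SD, with four time points and auto-correlation 0.2. With first-order autoregressive correlation, the variance of a four-point mean is [4 + 2(3×0.2 + 2×0.04 + 0.008)]/16 = 0.336. The standard error is √[0.336 × (1/20 + 1/40)] = 0.159, so 0.45/0.159 = 2.83 and two-sided power is about 81%. The figure reproduces, but it concerns questionnaire scores. No figure is given for hospital use.

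**Inputs for the count.** From the plan: 40 intervention and 20 control participants. Assumed, because the documents give no rates:
- 0.30 unplanned emergency episodes per control patient, half of them admitted, so 0.15 unplanned admissions
- a true workshop ratio of 0.60 on unplanned episodes
- S scheduled admissions per patient, equal in both arms and not passing through the emergency room

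**Hospitalization ratio as counted** = (0.60 × 0.15 + S)/(0.15 + S)

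| S per patient | Scheduled share of control admissions | Ratio as counted |
|---|---|---|
| 0 | 0 | 0.09/0.15 = 0.60 |
| 0.05 | 0.05/0.20 = 25% | 0.14/0.20 = 0.70 |
| 0.15 | 0.15/0.30 = 50% | 0.24/0.30 = 0.80 |
| 0.30 | 0.30/0.45 = 67% | 0.39/0.45 = 0.87 |

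The ratio equals 1 − 0.40 × (unplanned share of control admissions), so for a true ratio of 0.60 only that share matters, not the absolute rates.

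**Emergency-visit ratio** = (0.60 × 0.30)/0.30 = 0.18/0.30 = 0.60 for every S. This count is undiluted.

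**Adding the two counts, if anyone did so.** Let U be the unplanned emergency episodes per control patient and f the share of emergency visits that end in admission, equal in both arms. Without scheduled admissions the summed ratio is 0.60 × U(1 + f)/[U(1 + f)] = 0.60. Counting both ends of one episode does not by itself bias the ratio.

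**Power.** A Poisson simulation (40 against 20, 20,000 replicates, mean counts per patient compared with separate variances at a critical value of 2.0) used a true ratio of 0.60, U = 0.5 or 1.0 and S = 0.25 to 1.0.
- Unplanned episodes counted once: about 16% (U = 0.5) or 32% (U = 1.0)
- The same with emergency visits and their resulting admissions summed: about 14% or 29%
- Scheduled admissions added, each episode counted once: about 8–12% or 17–26%, with ratios of 0.68 to 0.87

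These runs use a combined count, which the plan does not specify, and more events than the table. At the table's rates only 40 × 0.09 = 3.6 and 20 × 0.15 = 3.0 unplanned admissions are expected, so the hospitalization comparison cannot be expected to do better.

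**The case against.** The strongest reply is that total use is a legitimate outcome. Sections 4.2 and 9.4.3 speak of frequency and number, not morbidity. The result in 5.1 belongs to a cited study and is not a stated rationale for this endpoint. The sentence in 15.2 that expects no effect on the cancer also suspects better adherence to therapy, and adherence might itself change scheduled admissions. This stands against dropping scheduled admissions. It does not stand against recording them separately, and if adherence matters it is a further reason to do so.

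The size is assumed. Recruitment is from outpatient clinics (7.7), and a current-treatment field does not show that treatment is given to inpatients. If scheduled admissions are rare, dilution is slight. That also stands, which is why a range is shown.

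A reader might go further in two ways that the documents do not support. One is that an emergency visit ending in admission scores as two events. No section adds the two counts. Reported apart, each is counted once and correctly, and even a sum would leave the ratio unbiased if the admitted share is equal in both arms. What is missing is a rule for a combined count, should one be used. The other is that the counting hides any workshop effect. The emergency-visit count, already planned, keeps the full 0.60 under the same assumptions, and the hospitalization count is diluted, not emptied.

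Chance imbalance with 20 controls is no special argument either, since it affects any count in this trial.

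**Conclusion.** The point holds for the hospitalization count. As defined, it pools scheduled and unplanned admissions, and no other section separates them. Under the assumed rates a true 0.60 would be seen as about 0.70 to 0.87. This rests on scheduled admissions being equal in both arms, unaffected by the workshop, and making up a quarter to two thirds of control admissions. None of this can be checked from the documents.

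The consequence is minor. The endpoint is exploratory in 9.4.3, no power claim depends on it, and the sample size limits it more than the counting rule does. The gain is an estimate that can be interpreted, not a well-powered test.

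**What to change.** In the chart review in 10.1, record for each admission whether it was scheduled or unscheduled and whether it came through the emergency room. In 9.4.3, state that emergency visits and unscheduled admissions are the between-arm comparisons, that scheduled admissions are tabulated separately by arm, and that the all-hospitalization total is kept alongside. State whether the counts are reported separately or combined. If combined, count an emergency visit that leads to admission as one episode. Settle this before arm totals are seen, so that the rule is not chosen after the fact.

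The cost is one or two abstraction fields in a review already planned, a few sentences of text, and fewer counted events in the main comparison. Power stays low either way.

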7.3 Key Inclusion Criteria

- Adult >20 years of age
- Any patient with a cancer diagnosis.
- Ability to understand English language and ability to write without any functional difficulty
- ECOG performance status 0-3

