9.2 Design

The focus of this study is to determine the difference in mental health parameters following the participation of cancer patients in a creative writing workshop. Participants will be randomized within strata formed by cancer type in order to assure that these potentially important confounding variables are balanced across groups. Patients will be enrolled on a rolling basis over a four to five-month period, allowing patients in intervention arm to participate in 2-3 months workshops (workshops would be held once every 2 weeks). Patients in control arm will be provided a book (*Writing Down Bones* by Natalie Goldberg) about creative writing and will be asked to do activities for 1.5 hours every 2 weeks. After three months, control group participants can join creative writing workshops at their discretion for the remaining period for writing workshops. Both group members will receive follow up surveys twice a month for two months at the completion of the participant's two-month study period.

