10.2 Clinical Covariates: Detailed clinical covariates will be obtained from questionnaires and medical record review including demographics (age, gender, race), cancer type and stage, psychiatric history, chemotherapy regimen and medication use.

10.3 Creative Workshop: Write from Heart: This workshop for cancer patients usually lasts one and a half hours and is broken into several parts. Usually beginning with inspirational quotes or passages from writings of respected authors, to shift mood and illuminated deeper thought and reflection. The next phase of the class consists of sharing a beautiful or whimsical object handed person to person or placed in the middle of the table to stimulate both curiosity and the senses. When participants are able to relax fully, in tranquil and focused surroundings the imagination easily transforms a bright polished stone or a glass heart with inner fractures into a metaphorical image. The technique of journaling is also encouraged in class, as a way to promote inner awareness to strengthen writing skills and to guide students to reach for their own comfort and consolation, when not in class. Within our setting, it is normal, though not mandatory that writing may lean toward the cancer experience. At the end of each series, students would have learned how to trust their artistic instincts, connect more courageously with

Institutional Review Board

the world of their emotions and transform their fears and revelations about cancer into words on the page.

10.4 Emotional Thermometers Scale: The Emotion Thermometers tool is a simple rapid modular screening tool for detection and monitoring of emotional disorders in clinical practice. It was created by [name] J Mitchell and has a simple visual-analogue design. It is easy for most patients (including older people) to understand, quick to administer and simple to score. We have already got permission from [name] J Mitchell for royalty free usage of this scale for 2 years starting from Aug, 2016 till Aug 2018. We will be getting permission from him to extend the usage for an additional 1-2 years.

10.5 Survey of Depression and Anxiety symptoms: For anxiety, we will use Generalized Anxiety Disorder 7-item (GAD-7) validated scale by Robert Spitzer et al. For depression we will use Patient Health Questionnaire 9-item (PHQ-9) validated scale by Robert Spitzer et al. Both of these scales do not require any permission for reproduction, display, distribution or usage.

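### Cancer status is compared between arms from one end-of-study reading, with no visible record of status at entry and two wordings for when the reading is taken

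*Combined protocol and SAP*

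**What the plan says.** References are to the current protocol text, which comes first in the combined file.

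- **The comparison.** Section 4.2 lists among the secondary objectives "Comparison of cancer status (stable, progressing, in remission) between intervention and control group". Section 9.4.3 lists the same item as exploratory: "Comparison of status of cancer (stable, progressing, in remission) between intervention and control group". Both concern status itself, not change from entry.
- **The reading.** Section 10.1 says "We will also review their most current cancer disease status after completion of the workshops". Table 1 (Demographics) in section 22 has a single status field: "Disease status at completion of study (Stable, Progression, Remission)".
- **Baseline data.** Section 10.1 says "we will collect baseline scores in both groups for each parameter as below"; these are questionnaire scores. Section 10.2 adds demographics and "cancer type and stage, psychiatric history, chemotherapy regimen and medication use". Table 1 adds ECOG status and current treatment. Section 11.1 uses time from diagnosis. None of these is stable, progressing or remission status at entry.
- **Who enters.** Section 7.3 admits "Any patient with a cancer diagnosis". Section 7.1 still describes new diagnosis or progression within three months. Entry status is mixed on either text.
- **Randomisation.** Patients are "randomized within strata formed by cancer type" (section 9.2), in a 2:1 ratio, 40 to 20 (section 11.2).
- **Analysis.** Section 11.1 names four groups of questionnaire outcomes and gives no method for cancer status.

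**The concern.** A status read only at the end mixes two things: where the patient started and what happened during the study. A patient in remission throughout is counted the same as one who reached remission. A patient who entered with progressing disease may be counted as progressing although nothing new occurred.

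If the arms happen to start with different mixes, the end table will show a difference that could be read as an effect on the cancer. Section 15.2 says no such effect is expected, so an apparent one would attract attention and be hard to explain without entry data. A real difference would also be harder to see, because variation in starting status stays in the comparison.

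The timing of the reading raises a second question. Control patients have no workshops of their own unless they choose to join later, so the wording in section 10.1 does not by itself fix a date for them.

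**Working it through.** **1. The plan's own figure.** The only design figure is in section 11.2: at least 80% power for 0.45 SD, with four time points and autocorrelation 0.2. With first-order autoregressive correlation:

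- variance of the mean = [4 + 2(3×0.2 + 2×0.04 + 0.008)]/16 = 0.336
- standard error = √0.336 × √(1/40 + 1/20) = 0.159
- power = Φ(0.45/0.159 − 1.96) ≈ 81%

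The figure reproduces, but it concerns the questionnaire scores. Nothing is stated for cancer status.

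**2. Chance imbalance in entry status.** Inputs: 40 and 20 patients (section 11.2). The share *p* with a given entry status is not in the documents, so it is assumed to lie between 10% and 50%. SD of the between-arm difference = √[p(1−p)(1/40 + 1/20)]; for p = 0.30, √(0.21 × 0.075) = 0.125. The probabilities are exact binomial.

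| p (assumed) | SD, points | P(gap ≥ 10 points) | P(gap ≥ 20 points) |
|---|---|---|---|
| 10% | 8.2 | 0.28 | 0.02 |
| 20% | 11.0 | 0.42 | 0.09 |
| 30% | 12.5 | 0.49 | 0.14 |
| 50% | 13.7 | 0.53 | 0.17 |

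The calculation ignores stratification by cancer type, which would reduce the gap to the extent that type predicts status.

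For scale, a raw comparison of 40 with 20 has 80% power (two-sided 0.05) only for differences of about 34 to 38 points, for example 10% versus 44% or 30% versus 68%.

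**3. Timing of the end reading.** Section 10.1 enrols through the first 4.5 months of a 6-month programme, so time from entry to programme end runs from 6 − 4.5 = 1.5 months to 6 months. There are two readings of the text.

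- *All charts are read at study end.* Follow-up varies from about 1.5 to 6 months, but with the same expected distribution in both randomised arms. No arm difference arises.
- *Each chart is read when that person finishes workshops.* The date is undefined for a control who never joins and can be later for one who does. Cumulative progression by month *t* is 1 − exp(−ht). The monthly hazard *h* is not in the documents, so 0.02, 0.05 and 0.10 are assumed. Reading at month 6 instead of month 2 adds 7.4, 16.4 and 27.0 points. That is an extreme. With uniform enrolment the mean time to programme end is 6 − 4.5/2 = 3.75 months, and reading then instead of at month 2 adds exp(−2h) − exp(−3.75h) = 3.3, 7.6 and 13.1 points. Even this assumes that every control joins and stays to the end while every workshop patient is read at month 2.

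**The case against.** Four objections have force.

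**Randomisation.** A reader might infer that the missing entry status biases the comparison. It does not. Allocation is random, so entry mix is balanced in expectation, and the SDs above are ordinary sampling error that a 0.05 test already allows for. What remains is that an imbalance, if it occurs, can be neither seen nor adjusted for. Stage, type, treatment and time from diagnosis are only partial substitutes.

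**Timing.** A reader might infer that workshop patients are read at about month 2 and controls as late as month 6. The more natural reading of section 10.1 is otherwise. The status sentence continues a review of all participants' charts at the end of the study, and Table 1 also says completion of study. Section 9.3 gives 2 to 6 months of participation without distinguishing arms. What remains is that the two wordings differ and no date or window is set.

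**Other evidence of worsening.** A reader might take this item as the trial's only check on deteriorating disease. Section 10.1 also counts emergency visits and hospitalisations, split into cancer-related and not. Cancer status is the only direct measure, not the only check.

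**Completeness of the record.** The list in section 10.2 is open-ended, and the schema, calendar and REDCap sample cannot be seen in this text. An entry-status item that appears only there cannot be ruled out. Against that, Table 1 does list the participant-level fields, and its only status field is labelled as an end reading.

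**Conclusion.** The point holds in a limited form. From what can be seen, status is compared between arms on one end reading with no entry status. The comparison therefore cannot separate unchanged disease from new progression or new remission. A chance entry gap of 10 points or more has probability about 0.28 to 0.53, on the assumption that 10% to 50% of patients share a given entry status. That costs precision and interpretability.

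The documents do not support a claim of systematic bias from entry mix. They also do not establish a difference in reading time between arms; that would arise only if the reading were tied to each person's own workshop completion. The inconsistent wording should still be reconciled.

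Priority is low to moderate. Section 9.4.3 labels the endpoint exploratory (section 4.2 lists it under secondary objectives, which should also be aligned), section 15.2 expects no effect on cancer, and no sample size or primary conclusion depends on it.

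**What to change.** 1. **Entry status.** Add disease status at enrolment, with its date, to Table 1 and section 10.2, taken from the medical record review already planned. Because it comes from the chart, it can be completed for patients already enrolled, using entries dated before randomisation.
2. **End reading.** Reconcile section 10.1 and Table 1 to one rule that does not depend on arm or workshop attendance, and record the date of the status used.
3. **Comparison.** In section 9.4.3, replace raw end status with a comparison adjusted for entry status, for example new progression since entry (yes or no) by arm. State how a patient who enters with progressing disease is counted, and add a line on the method to section 11.1. A full table of entry by end status by arm has 3 × 3 × 2 = 18 cells for 60 patients, which is too sparse to be the main analysis.

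The cost is one dated field per patient from a chart that is already opened, plus wording changes. No extra visits or patients are needed. There is no need to require that the reading precede the point at which controls may join workshops; such an early date could miss the most recent assessment in the chart.
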